7.1.7.2. Study Drug Related Injection Site Induration and Nodules

Percentage of ongoing and resolved study drug related “Injection Site Induration” (one of preferred terms of ISR) will be summarized at both participant-level and event-level.

For the participant-level summary, if a participant had more than one injection site indurations, the participant will be counted in the “Ongoing” category unless all study drug related injection site induration events have been resolved.

For the event-level summary, duration of the resolved events will be summarized using descriptive statistics.

Study drug related “Injection Site Nodules” (another preferred term of ISR) will be summarized in the same manner as defined for study drug related injection site induration.

A by-participant listing for study drug related injection site induration and nodules and the corresponding duration will be provided.

7.2. Laboratory Evaluations

Summaries of laboratory data will be provided for the whole study period and LA regimen period analysis, respectively. Laboratory data collected during the study will be analyzed and summarized using both quantitative and qualitative methods.

For whole study period analysis, summaries of laboratory data will be provided for the Safety Analysis Set and will include data collected up to the last exposure date for participants who have permanently discontinued study, or all available data at the time of the database snapshot for participants who were ongoing on study at the time of an interim analysis.

For LA regimen analysis, summaries of laboratory data will be provided for the Safety Analysis Set for LA regimen and will include data collected up to the last exposure date of LA regimen for participants who have permanently discontinued study drug, or all available data at the time of the database snapshot for participants who were ongoing on study drug at the time of an interim analysis.

Calcium Corrected for Albumin

Calcium corrected for albumin will be calculated and summarized for the study. The following formula will be used when both serum calcium and albumin results for a given blood drawn are available and serum albumin value is < 4.0 g/dL.

Calcium corrected for albumin (mg/dL) = serum calcium (mg/dL) + $0.8 \times (4.0 - \text{albumin (g/dL)})$

Toxicity grading for calcium will be applied based on the corrected values.

Estimated Glomerular Filtration Rate

The following formulae will be used to calculate the estimated glomerular filtration rate using Cockcroft-Gault formula (eGFR_{CG}):

$$\text{eGFR}_{\text{CG}} (\text{mL/min}) = [(140 - \text{age (yrs)}) \times \text{weight (kg)} \times (0.85 \text{ if female})] / (\text{SCr (mg/dL)} \times 72),$$

where weight is total body mass in kilograms and SCr is serum creatinine.

The analysis will be based on values reported in conventional units. When values are below the LLOQ, they will be listed as such, and the closest imputed value will be used for the purpose of calculating summary statistics as specified in Section 3.7.

No formal statistical testing is planned.

7.2.1. Summaries of Numeric Laboratory Results

Descriptive statistics will be provided by treatment group for selected laboratory test as follows:

- Baseline values
- Values at each postbaseline visit
- Change from baseline at each postbaseline visit

A baseline laboratory value will be defined as the last measurement obtained on or prior to the date of first dose of study drug. Change from baseline to a postbaseline visit will be defined as the visit value minus the baseline value. The mean, median, Q1, Q3, minimum, and maximum values will be displayed to the reported number of digits; SD values will be displayed to the reported number of digits plus 1.

In the case of multiple values in an analysis window, data will be selected for analysis as described in Section 3.8.3.

7.2.2. Graded Laboratory Values

The DAIDS Table for Grading the Severity of Adult and Pediatric Adverse Events, Version 2.1 dated July 2017, will be used to assign toxicity grades (0 to 4) to laboratory results for analysis. Grade 0 includes all values that do not meet the criteria for an abnormality of at least Grade 1. For laboratory tests with criteria for both increased and decreased levels, analyses for each direction (ie, increased, decreased) will be presented separately.

For triglycerides, LDL (4th generation), and cholesterol, toxicity grading scale is for fasting test values, so nonfasting lipid results (or lipid results without a known fasting status) will not be graded or summarized by toxicity grades.

7.2.2.1. Treatment-Emergent Laboratory Abnormalities

For whole study period analysis, treatment-emergent laboratory abnormalities are defined as values that increase at least 1 toxicity grade from baseline at any postbaseline visit, up to last exposure date for participants who permanently discontinued study, or the last available date in the database snapshot for participants who were still on study at the time of an interim analysis.

For LA regimen period analysis, treatment-emergent laboratory abnormalities are defined as values that increase at least 1 toxicity grade from baseline at any postbaseline visit, up to last exposure date of LA regimen for participants who permanently discontinued study drug, or the last available date in the database snapshot for participants who were still on treatment at the time of an interim analysis.

If the relevant baseline laboratory value is missing, any abnormality of at least Grade 1 observed at any postbaseline visit will be considered treatment emergent.

7.2.2.2. Summaries of Laboratory Abnormalities

Laboratory data that are categorical will be summarized using the number and percentage of participants in the study with the given response at baseline and each scheduled postbaseline visit.

The following summaries (number and percentage of participants) for treatment-emergent laboratory abnormalities will be provided by lab test and treatment group; participants will be categorized according to the most severe postbaseline abnormality grade for a given lab test:

- Graded laboratory abnormalities
- Grade 3 or 4 laboratory abnormalities

For all summaries of laboratory abnormalities, the denominator is the number of participants with nonmissing postbaseline values.

A by-participant listing of treatment-emergent laboratory abnormalities and treatment-emergent Grade 3 or 4 laboratory abnormalities, respectively, will be provided by participant ID number and visit in chronological order. This listing will include all test results that were collected throughout the study for the lab test of interest, with all applicable severity grades and abnormal flags displayed.

7.3. Body Weight and Vital Signs

Descriptive statistics will be provided by treatment group and total for body weight, BMI and vital signs as follows:

- Baseline value
- Values at each postbaseline visit
- Change from baseline at each postbaseline visit

A baseline value will be defined as the last available value collected on or prior to the first dose date of study drug. Change from baseline to a postbaseline visit will be defined as the postbaseline value minus the baseline value.

In the case of multiple values in an analysis window, data will be selected for analysis as described in Section 3.8.3. No formal statistical testing is planned.

A by-participant listing of vital signs will be provided by participant ID number and visit in chronological order. Body weight, height, and BMI will be included in the vital signs listing, if space permits. If not, they will be provided separately.

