Optional Pharmacogenomic Sample ^j															

- For the Primary Cohort, screening procedures will be conducted in 2 parts: Part 2 will be performed once results of bNAb sensitivity testing from Part 1 are reviewed and participant is deemed eligible to proceed. For the optional Pilot Cohort, participants will be selected by the sponsor from the previously screened/failed participants in the Primary Cohort and will directly proceed to Screening Part 2 (no need to repeat Screening Part 1).
- Refer to Section 6.5.1 for Post-ET 30-, 90-, and 180-Day follow-up visits.
 - Counsel participant regarding the importance of continuing a complete ARV therapy in accordance to standard of care, and refer patient to an appropriate HIV treatment facility.
- Vital signs: blood pressure, pulse, respiration rate, and temperature. On Day 1, vital signs should be recorded prior to start of study drug administration and 30 minutes (± 10 minutes) after completion of the GS-2872 infusion.
- Serum FSH test (required for female participants < 54 years of age who have stopped menstruating for ≥ 12 months but do not have documentation of ovarian hormonal failure; see Appendix 5)
- HIV-1 genotype and phenotype testing for participants with virologic failure. Refer to Section 6.8.2.
- PK serum samples will be collected in all participants for GS-5423 and GS-2872 as follows:
 - The exact time of study drug administration and the exact time points (date and time) of collection of plasma samples must be carefully recorded.
 - Day 1: 0 hour (predose, ≤ 30 minutes prior to dosing of oral LEN for loading), within 5 minutes after the end of the first antibody infusion (GS-5423) and within 5 minutes after the end of the second antibody infusion (GS-2872)
 - For ET visit, only single PK sample collection is required

- g. PK plasma samples for LEN will be collected in all participants as follows:
- PK samples should be drawn from a separate catheter in the opposite arm from the one used for GS-5423 and GS-2872 IV infusion to avoid contamination.
 - Day 1: 0 hour (predose, ≤ 30 minutes prior to dosing of oral LEN for loading), within 5 minutes after the end of the first antibody infusion (GS-5423) and within 5 minutes after the end of the second antibody infusion (GS-2872)
 - For ET visit, only single PK sample collection is required
- h. Participants will take oral LEN for loading on Day 1 at the clinic and self-administer on Day 2 at home, unless participating in the Optional PK Substudy.

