3.8.1. Definition of Key Dates and Study Day

Study Day 1 is defined as the day when the first dose of any study drug was taken, as recorded on the Study Drug Administration eCRF (ie, oral LEN, SC LEN or infusion drugs [GS-5423, GS-2872]).

Last Dose Date is defined as the latest dose date of any study drug as recorded on the Study Drug Administration eCRF (ie, oral LEN, SC LEN or infusion drugs (GS-5423, GS-2872) for participants who prematurely discontinued study drug or completed study drug according to Study Drug Completion eCRF.

Study Days are calculated relative to Study Day 1 of study drug and derived as follows:

- For postdose study days: Assessment Date – First Dose Date + 1
- For days prior to the first dose: Assessment Date – First Dose Date

Baseline Value is defined as the last value obtained on or prior to the first dose of study drug.

Last Study Date is the latest clinic visit dates, and/or the laboratory visit dates, whichever is latest, including the any follow-up visit dates, for participants who prematurely discontinued study or completed study according to the Study Completion eCRF.

Last Exposure Date is defined as follows for participants who prematurely discontinued study or complete study according to Study Completion eCRF (i.e. participant answered “No” or “Yes” for “Did the participant complete the protocol-planned duration of the study” on Study Completion form):

- For participants who receive any injection or infusion, last exposure date is defined as last study date.
- For participants who do not receive any injection or infusion (i.e. for those who only receive oral LEN), last exposure date is defined as the earliest of the last dose date plus 60 days and the last study date.

The last exposure date is defined considering the prolonged exposure of LEN, GS-5423, and GS-2872 after the last dose date of LEN, GS-5423, and GS-2872 through the end of study.

Last Exposure Date of LA Regimen is defined as follows for participants who prematurely discontinued study drug or complete study drug according to Study Drug Completion eCRF (i.e. participant answered “No” or “Yes” for “Did participant complete study drug dosing as specified per protocol” on Study Drug Completion form):

- the earliest date of last study day or ART restart day for participants who prematurely discontinued study or complete study, or

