- For baseline, the last nonmissing value on or prior to the first dose date of study drug will be selected, unless specified differently. If there are multiple records with the same time or no time recorded on the same day, the baseline value will be the average of the measurements for continuous data (except for HIV-1 RNA, see below), or the measurement with the lowest severity (eg, normal will be selected over abnormal for safety ECG findings) for categorical data.
- For postbaseline values:
 - The record closest to the nominal day for that visit will be selected with the exception of CD4 cell counts, CD4%, and CD8 cell count in which the latest record will be selected and HIV-1 RNA level (see below).
 - If there are 2 records that are equidistant from the nominal day, the later record will be selected.
 - If there is more than 1 record on the selected day, the average will be taken for continuous data (except for HIV-1 RNA, see below) and the worse severity will be taken for categorical data, unless otherwise specified.
- For baseline HIV-1 RNA, the latest (considering both date and time) record(s) on or prior to the first dose date and time of study drug will be selected.
- For postbaseline HIV-1 RNA, the latest (considering both date and time) record(s) in the window will be selected.
 - If both “HIV RNA COBAS 6800” and “HIV RNA TAQMAN 2.0” are available with the same collection time, the results from the “HIV RNA COBAS 6800” will be selected for analysis purpose.
 - If both “HIV COBAS 6800” and “HIV RNA REPEAT COBAS” (ie, the HIV-1 RNA result obtained from an additional aliquot of the original sample) are available with the same collection time, the results from the “HIV RNA REPEAT COBAS” will be selected for analysis purposes; otherwise, if there are multiple “HIV COBAS 6800” records with the same collection time, the geometric mean will be taken for analysis purposes.
 - If both “HIV RNA TAQMAN 2.0” and “HIV RNA Repeat” are available with the same collection time, the results from the “HIV RNA Repeat” will be selected for analysis purposes; otherwise, if there are multiple “HIV RNA TAQMAN 2.0” records with the same collection time, the geometric mean will be taken for analysis purposes.

If multiple valid nonmissing categorical observations exist in a window, records will be chosen as follows:

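### The SAP's date-based vital-sign baseline (7.3, 3.8.3) conflicts with the dose-based one (3.8.1) and, read literally, selects the post-infusion Day 1 reading

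*SAP*

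**What the plan says.** Protocol Appendix 2 (footnote on vital signs) and Protocol 6.4.1 schedule two sets of Day 1 readings: "vital signs should be recorded prior to start of study drug administration and 30 minutes (± 10 minutes) after completion of the GS-2872 infusion". Protocol 5.3 requires all Day 1 drugs to be given on the same day.

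The SAP gives three baseline rules that bear on this:

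- SAP 7.3, the section on vital signs: "A baseline value will be defined as the last available value collected on or prior to the first dose date of study drug".
- SAP 3.8.3, the record-selection rule to which 7.3 refers: "For baseline, the last nonmissing value on or prior to the first dose date of study drug will be selected, unless specified differently". It adds a tie rule. "If there are multiple records with the same time or no time recorded on the same day", continuous values are averaged.
- SAP 3.8.1, the general definition: "Baseline Value is defined as the last value obtained on or prior to the first dose of study drug".

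For HIV-1 RNA alone, 3.8.3 is explicit about time of day: "the latest (considering both date and time) record(s) on or prior to the first dose date and time of study drug will be selected".

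SAP Table 3-3 closes the baseline window for vital signs at Day 1 and opens the Week 4 window at Day 2.

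**The concern.** Two of the three rules turn on a calendar date, and that date contains both a predose and a postdose measurement. Taking the last value on the date means taking a value recorded after the oral and subcutaneous lenacapavir and both antibody infusions. A baseline should not contain a response to treatment. If it does, any acute change in blood pressure, pulse, respiration or temperature is built into the reference value and returns with opposite sign at every later visit.

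The randomized groups differ only in the GS-2872 dose, and the second reading is timed from the end of that infusion. If the acute change differed by dose, the two groups' baselines would be displaced by different amounts, and so would the comparison of their later changes.

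**Working it through.** The plan states no figure on this point, so there is none to reproduce. The check has four steps.

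**1. Is the second reading always after the first dose, and on the same date?** Inputs are Protocol 3.3 (each infusion lasts 60 minutes), Protocol 5.3 (the gaps between drugs) and Appendix 2 (30 ± 10 minutes after the GS-2872 infusion). I assume that the injections take 0 to 15 minutes and that the infusions are not interrupted. Minutes from oral lenacapavir to the second reading:

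| Step | Shortest | Longest |
|---|---|---|
| Oral to SC lenacapavir | 0 | 30 |
| SC injections | 0 | 15 |
| Gap to GS-5423 | 0 | 60 |
| GS-5423 infusion | 60 | 60 |
| Gap to GS-2872 | 15 | 60 |
| GS-2872 infusion | 60 | 60 |
| Wait to vital signs | 20 | 40 |
| **Total** | **155** | **325** |

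The reading comes 155/60 = 2.6 to 325/60 = 5.4 hours after the first dose, on the first dose date.

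**2. What does each rule select?** Let the predose value be b, the post-infusion value b + d, and a later visit value v. The correct change is v − b.

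- 7.3 and 3.8.3, times recorded: baseline = b + d, reported change = v − b − d, error = −d.
- 3.8.3, times not recorded: baseline = (b + b + d)/2 = b + d/2, error = −d/2.
- 3.8.1: baseline = b, error = 0.

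**3. Illustration.** The values of d are assumed, because the documents give none. Take systolic pressure 120 mmHg predose and 120 at Week 4, so the correct change is 0:

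| d (mmHg) | Reported change, date rule | Averaged | Dose rule |
|---|---|---|---|
| −10 | +10 | +5 | 0 |
| −5 | +5 | +2.5 | 0 |
| +5 | −5 | −2.5 | 0 |
| +10 | −10 | −5 | 0 |

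The same shift applies at every later visit. If the mean acute changes in the two groups are d1 and d2, the date rule moves the difference in mean change (group 2 minus group 1) by −(d2 − d1).

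**4. Would the right baseline bring the acute change into the tables?** SAP 3.8.1 computes study day from dates, so the post-infusion reading is on Study Day 1. Table 3-3 assigns Day 1 to baseline and starts Week 4 at Day 2. The reading therefore has no postbaseline slot under any of the three rules.

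**The case against.** The strongest reply is that the SAP's general definition, 3.8.1, already gives the predose value, and that the HIV-1 RNA rule shows the authors know the distinction. A reader might infer from 7.3 that the SAP has settled on a post-infusion baseline, but the documents do not support that: they contain two incompatible rules and do not say which prevails. This stands as a limit on certainty. It does not remove the problem, because 7.3 is the text specific to vital signs, it points to 3.8.3, which has the same date wording, and it is the likelier one to be programmed.

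A reader might also infer that the plan conceals acute infusion effects. It does not. SAP 7.3 provides a chronological by-participant listing of vital signs, and SAP 7 puts all collected data in listings, which are workable with about 20 Primary Cohort and up to 20 Pilot Cohort participants. SAP 7.1.7.1 summarizes study-drug-related infusion reactions by grade and preferred term. Protocol 7.6 requires abnormal vital signs associated with signs or symptoms to be recorded as adverse events if they meet the definition. What is left uncovered is a group-level summary of acute change, chiefly asymptomatic change.

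Finally, Protocol 8.6.4 promises only a summary of vital signs by treatment group, so omitting a 30-minute change is partly a choice of presentation. That is fair. The added row is a recommendation that follows from the schedule, whereas the conflict between baseline rules has to be resolved in any case.

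**Conclusion.** The point holds as an internal contradiction in which one side gives a wrong result. Read literally, SAP 7.3 and 3.8.3 use a postdose reading, or an average that includes it, as the vital-sign baseline. SAP 3.8.1 does not.

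The size is −d per participant at each later visit, or −d/2 if the two readings are averaged, where d is that participant's acute change. The documents give no value for d. If it is typically near zero, mean changes barely move.

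The shift requires that the date rule is the one applied and that a post-infusion record exists. The documents do not say whether vital-sign times or predose labels are captured, so which branch of the date rule applies is unknown. It would therefore be too strong to say that every change from baseline is wrong. SAP 7.3 plans no formal testing of these data. The primary endpoint, treatment-emergent SAEs through Week 26, does not use them. Weight and BMI are unaffected because weight is scheduled only before dosing on Day 1.

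The missing Day 1 post-infusion summary is a separate gap caused by Table 3-3, and correcting the baseline alone would not close it.

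**What to change.** In SAP 7.3 and 3.8.3, define the vital-sign baseline as the last nonmissing value before the date and time of the first dose of any study drug, in line with 3.8.1 and the HIV-1 RNA rule. Where a time is missing, use the predose time-point label; do not average predose and postdose readings.

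Add a Day 1, 30 minutes post-infusion row to the vital-sign summary, with change from the predose value, and exempt it from the Day 1 baseline window in Table 3-3.

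The cost is a wording change in two sections, a note to Table 3-3 and one table row. Both readings are already scheduled, and Protocol 5.3 already requires exact dosing times in the source document, so no new assessment is needed. If the SAP is already final, SAP 1 provides for documenting the change in the clinical study report.

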7.4. Prior and Concomitant Medications

Medications collected at screening and during the study will be coded using the current version of the World Health Organization (WHO) Drug dictionary. The WHO preferred name and drug code will be attached to the clinical database.

7.4.1. Nonstudy Drug Antiretroviral Medications

Any nonstudy drug ARV medications used prior to, during, or after the study (if collected) will be listed. No inferential statistics will be provided.

Antiretroviral medications at baseline will be summarized by ARV category and drug name. Antiretroviral medications at baseline are defined as the ARV medications taken on or up to 2 day prior to first dose date of study drug.

